5.5.1 Duration of overall response

The duration of overall response is measured from the time measurement criteria are met for CR or PR (whichever is first recorded) until the first date that recurrent or progressive disease is objectively documented (taking as reference for

progressive disease the smallest measurements recorded since the treatment started).

The duration of overall CR is measured from the time measurement criteria are first met for CR until the first date that progressive disease is objectively documented.

5.5.2 Duration of stable disease

Stable disease is measured from the start of the treatment until the criteria for progression are met, taking as reference the smallest measurements recorded since date of study entry, including the baseline measurements.

5.6 **Progression-Free Survival**

Progression-Free Survival (PFS) is defined as the duration of time from study entry to time of progression or death, whichever occurs first.

5.7 Survival

Survival is defined as the duration of time from study entry to time of death or the date of last contact.

6 DRUG INFORMATION

6.1 Tivozanib Hydrochloride

- 6.1.1 Other Names AV-951
- 6.1.2 Classification VEGFR tyrosine kinase inhibitor
- 6.1.3 Molecular Formula and Weight C₂₂H₁₉ClN₄O₅ HCl H₂O 509.34 (hydrochloride monohydrate) 454.86 (free base)
- 6.1.4 Chemical Name N-{2-Chloro-4-[(6,7-dimethoxy-4-quinolinyl)oxy]phenyl}-N'-(5-methyl-3isoxazolyl) urea hydrochloride monohydrate
- 6.1.5 Mechanism of Action:

Tivozanib is a highly potent inhibitor of vascular endothelial growth factor (VEGF) receptor tyrosine kinases (VEGFR1, VEGFR2, and VEGFR3). Vascular endothelial growth factor receptor inhibition may block VEGF driven angiogenesis and, as a consequence, constrain tumor growth.

 6.1.6 Drug Storage and Stability Tivozanib hydrochloride drug product should be stored at room temperature (15°–25°C) in a controlled access room that can be entered only by authorized pharmacy or investigative personnel.

Long-term stability studies conducted according to ICH guidelines support an expiration dating of 36 months for dose strengths ranging from 0.5 mg to 2.0 mg when stored at 15-25°C with allowable excursions up to 30°C. Tivozanib hydrochloride drug product is an investigational new drug. Accordingly, all drug handling and disposal procedures for orally administered investigational drugs should be performed by qualified personnel as documented by the American Hospital Formulary Service or other recognized formulary requirements.

6.1.7 Protocol Dose

The following dosage strengths will be made available:

1.5 mg

1.0 mg

The amount of study drug dispensed to the subject at the beginning of each dosing cycle will be sufficient to allow for 3 weeks (21 days) of consecutive once-daily dosing of tivozanib hydrochloride. Dosing compliance will be monitored at each clinic visit.

- 6.1.8 Route of Administration Tivozanib hydrochloride is formulated for oral administration as a white opaque number 4 gelatin capsule.
- 6.1.9 Availability Provided at free of charge by AVEO Pharmaceuticals, Inc.

6.1.10 Approximate Solubility

Practically insoluble in water, slightly soluble in methanol, very slightly soluble in ethanol, and freely soluble in dimethyl sulfoxide.

Complete study drug information (including packaging, labeling, storage and disposition) is provided in the Tivozanib Hydrochloride Investigator's Brochure (IB).

7 CLINICAL AND LABORATORY EVALUATIONS

7.1 Schedule of Assessments

Paramatar	Pre-	Weekly	Prior to	Every Odd	End of Treatment Visit	Follow Un
i ai ainctci	Therapy	Day)	(-4 Days)	Days)	$(\pm 14 \text{ Days})^{12}$	ronow op
History and Physical Exam	X ²		X	• /	· · · · ·	
Vital signs (Blood Pressure, Heart Rate and Temperature)	X ²	X	X			
ECOG Performance Status	X ²		Х			
Toxicity Assessment ⁵	X ²	X^4	Х		Х	
CBC/Differential/Platelets	X ²	X ³	X ⁶			
PT/INR and PTT	X ^{2,7}					
$CMP + electrolytes^{14}$	X ²	X ³	X ⁶			
Total bilirubin, AST, ALT, Alkaline Phosphatase	X ²	X ³	X ⁶			
Urine Pregnancy Test (if childbearing potential	\mathbf{V}^2					
exists)	Λ					
X-ray or CT or MR imaging	X ¹			X^{11}	X ¹¹	
(chest/abdomen/pelvis)				11	11	
Radiographic tumor measurement	X ¹			X ¹¹	X ¹¹	
CA-125	X^1		X ¹⁵			
Electrocardiogram (ECG)	X^1		X ¹⁵			
Echocardiogram (ECHO) / MUGA	X ¹					
Urinalysis to evaluate for proteinuria	X ⁸			X ^{9, 10}		
Patient Tablet Calendar			Х			
Follow-up Phone Call		X^4				
Review Con Meds ¹⁶	X ²		Х		Х	X^{16}
Survival Status						X ¹³

One cycle = 28 days

- 1. Must be obtained within 28 days prior to study registration.
- 2. Must be obtained within 7 days prior to study registration.
- 3. During the first two cycles of therapy patients should have CBC and CMP performed weekly while taking study medication. Magnesium and Phosphorus are only required weekly during the first two cycles if clinically indicated. Thereafter the patient can be seen prior to each cycle.
- 4. Weekly toxicity assessment performed during for cycle 1 only. Assessment can be done at a clinic visit, by phone or by email.
- 5. Report all adverse events that occur within 30 days of last protocol treatment of therapy administered.
- 6. Must be obtained within 4 days of treatment with protocol therapy.
- 7. Patients on prophylactic or therapeutic anticoagulation with warfarin should have PT/INR monitored after starting and stopping tivozanib (e.g., weekly for the first cycle and weekly for a minimum of 2 weeks following discontinuation of tivozanib) and weekly for the first cycle of treatment following a warfarin or tivozanib dose modification.
- 8. Urinalysis to evaluate for proteinuria must be obtained 14 days prior to initiating protocol therapy.
- 9. If protein is 3+ or higher (≥ 300 mg/dL), 24-hour urine protein should be obtained and the level must be <1000 mg (<1g/24hrs) for patient to continue on study.
- 10. Urinalysis to evaluate for proteinuria should be performed prior to every odd cycle (for example, prior to cycles 1, 3, 5, 7, ETC).
- 11. CT scan or MRI or x-ray of chest-abdomen-pelvis every other cycle (or equivalent time frame for patients off treatment prior to disease progression) for the first 6 months; then every 3 months thereafter until disease progression; also repeat at any other time if clinically indicated based on symptoms or physical signs suggestive of progressive disease; also complete at the end of treatment if clinically indicated. Responses (CR and PR) require confirmation at greater than or equal to 4 weeks from initial documentation (see section 8).
- 12. End of treatment visit will occur within ± 14 days of the decision to discontinue study treatment.
- 13. Follow-up approximately 30 days after the last dose of Tivozanib and then approximately every 3 months for 2 years and then every 6 months for 3 years.
- 14. CMP + electrolytes includes: Sodium, potassium, chloride, bicarbonate, BUN, Glucose, Albumin, Creatinine, Calcium, Magnesium, Phosphorus, total protein. Magnesium and Phosphorus are only required if clinically indicated
- 15. Must be completed within 14 days prior to each cycle. Exceptions include treatment delays, in which case they would be allowed within 21 days prior to the delayed cycle.
- 16. Record all reported concomitant medications from the time of consent until 30 days after the last dose of Tivozanib (or until initiating the next line of anti-cancer therapy, whichever is first).

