grade 3 fatigue, and grade 3 dyspnea. Given these toxicities, an expansion cohort including 12 patients treated at 1.0 mg daily was assessed. With respect to efficacy, two patients with mRCC had partial responses (one confirmed, one unconfirmed), whereas the majority of patients in the study (55.2%) had stable disease as a best response. Eight patients (20%) received therapy for more than 9 months. PK analyses accompanying the study showed a mean half-life of 4.7 days (range, 1.3 to 9.7 days). The time to achieve maximum serum concentration (tmax) was between 2 and 24 hours. Other correlative studies showed that although VEGF-A levels rose consistently at the start of tivozanib therapy in a dose-dependent manner, these levels normalized after 14 days off therapy. In contrast, sVEGFR2 levels were reduced with increasing doses of tivozanib with the most marked decrease noted toward the end of the cycle (i.e., a larger decrease was observed at day 27 of therapy versus day 14). Dynamic contrast-enhanced MRI (DCE-MRI) was performed in a small subset of patients enrolled in the study (n = 8). Consistent with pre-clinical observations, a decrease in tumor vessel density was observed over time [7].

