9.1 Adverse Event Monitoring

Adverse event data collection and reporting, which are required as part of every clinical trial, are done to ensure the safety of subjects enrolled in the studies as well as those who will enroll in future studies using similar agents. Adverse events are reported in a routine manner at scheduled times during a trial (see Section 7 for timepoints). In addition, certain adverse events must be reported in an expedited manner to allow for optimal monitoring and patient safety and care.

All patients experiencing an adverse event, regardless of its relationship to study drug, will be followed until:

- the adverse event resolves or the symptoms or signs that constitute the adverse event return to baseline;
- any abnormal laboratory values have returned to baseline;
- there is a satisfactory explanation other than the study drug for the changes observed; or
- death.

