9.2.2 Severity of AEs

Note, some hematology studies may choose to grade toxicity using alternatives to the CTCAE v4.03 (e.g., iwCLL criteria). When an alternative is used, please modify this section as needed. If using the CTCAE state:

All non-hematologic adverse events will be graded according to the NCI Common Terminology Criteria for Adverse Events (CTCAE) version 4.03. The CTCAE v4.03 is available at http://ctep.cancer.gov/reporting/ctc.html.

If no CTCAE grading is available, the severity of an AE is graded as follows:

- Mild (grade 1): the event causes discomfort without disruption of normal daily activities.
- Moderate (grade 2): the event causes discomfort that affects normal daily activities.
- Severe (grade 3): the event makes the patient unable to perform normal daily activities or significantly affects his/her clinical status.
- Life-threatening (grade 4): the patient was at risk of death at the time of the event.
- Fatal (grade 5): the event caused death.
- 9.2.3 Serious Adverse Events (SAEs)

All SAEs, regardless of attribution, occurring from time of signed informed consent, through 30 days after the last administration of study drug, must be reported upon discovery or occurrence.

An SAE is defined in regulatory terminology as any untoward medical occurrence that:

• Results in *death*.

If death results from (progression of) the disease, the disease should be reported as event (SAE) itself.

• Is life-threatening.

The patient was at risk of death at the time of the event; it does not refer to an event that hypothetically might have caused death if it were more severe.

• Requires in-patient hospitalization or prolongation of existing hospitalization for ≥ 24 hours.

- Results in persistent or significant disability or incapacity.
- Is a congenital anomaly/birth defect.
- Is an important medical event.

Any event that does not meet the above criteria, but that in the judgment of the investigator jeopardizes the patient, may be considered for reporting as a serious adverse event. The event may require medical or surgical intervention to prevent one of the outcomes listed in the definition of "Serious Adverse Event".

For example: allergic bronchospasm requiring intensive treatment in an emergency room or at home; convulsions that may not result in hospitalization; development of drug abuse or drug dependency.

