9.3.2 Determining if Expedited Reporting is Required

This includes all events that occur within 30 days of the last dose of protocol treatment. Any event that occurs more than 30 days after the last dose of treatment and is attributed (possibly, probably, or definitely) to the agent(s) must also be reported accordingly.

- 1) Identify the type of adverse event using the NCI CTCAE v 4.03.
- 2) Grade the adverse event using the NCI CTCAE v 4.03.
- 3) Determine whether the adverse event is related to the protocol therapy. Attribution categories are as follows:

Definite: AE is clearly related to the study treatment. Probable: AE is likely related to the study treatment. Possible: AE may be related to the study treatment. Unlikely: AE not likely to be related to the study treatment. Unrelated: AE is clearly NOT related to the study treatment.

4) Determine the prior experience of the adverse event.

Expected events are those that have been previously identified as resulting from administration of the agent. An adverse event is considered unexpected, for

expedited reporting purposes only, when either the type of event or the severity of the event is not listed in:

- the current protocol
- the drug package insert
- the current Investigator's Brochure

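### Adverse events are reportable for 30 days after the last dose, but the last scheduled toxicity assessment is an end-of-treatment visit tied to the decision to stop, so new events after it are not asked about

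*Combined protocol and SAP*

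**What the plan says.** Three places set a 30-day window after the last dose. Footnote 5, attached to the Toxicity Assessment row of the Section 7.1 schedule, says: "Report all adverse events that occur within 30 days of last protocol treatment of therapy administered". Section 9.2.3 covers serious events "occurring from time of signed informed consent, through 30 days after the last administration of study drug". Section 9.3.2, on expedited reporting, states: "This includes all events that occur within 30 days of the last dose of protocol treatment".

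Section 9.1 says how routine events are gathered: "Adverse events are reported in a routine manner at scheduled times during a trial (see Section 7 for timepoints". In that schedule, Toxicity Assessment is marked before therapy, weekly (cycle 1 only, footnote 4), before each cycle, and at the end-of-treatment visit. The Follow-Up cell of the row is empty.

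Footnote 12 sets the timing of the last of these: "End of treatment visit will occur within ± 14 days of the decision to discontinue study treatment". Section 4.5 agrees. Footnote 13 then provides a later contact: "Follow-up approximately 30 days after the last dose of Tivozanib". The Follow-Up column assigns only concomitant medication review and survival status to it. Section 4.5 counts the 30 days to this contact from discontinuation of treatment, where footnote 13 counts from the last dose.

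Section 8 lists toxicity as a secondary objective, with grades summarized by counts and frequencies.

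**The concern.** The reporting duty runs from the last dose, but the last scheduled question about toxicity runs from a different date. On this schedule the decision to stop can come on a dosing day, at the end of the rest week, or after a hold. The end-of-treatment visit may therefore fall early in the 30-day window, or before it opens. The patient is contacted again near day 30, but the schedule then asks about medications and survival, not about new adverse events.

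At stake is the completeness of a secondary endpoint. A new non-serious event that starts after the end-of-treatment visit is in scope under footnote 5, but no scheduled assessment looks for it. If such events are missed, the toxicity counts are too low. With 30 patients, each patient missed moves a patient-level rate by 1/30, or 3.3 percentage points.

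**Working it through.** The plan gives no figure to reproduce here, so the check is calendar arithmetic.

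**Inputs**
- Window: 30 days after the last dose (footnote 5; Sections 9.2.3 and 9.3.2).
- L, days from last dose to the decision to stop. This is my assumption, taken from the dosing rules: 0 (stopped on a dosing day), 7 (decision at the end of the rest week, Section 4.2.2), 14 (after the two-week interruption allowed in the notes to the Section 4.7.1 table).
- V, day of the end-of-treatment visit relative to the decision: −14 to +14 (footnote 12).

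**Formula**

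Days of the window after the last scheduled assessment: U = 30 − min(30, max(0, L + V)).

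| L | Visit on decision day (V = 0) | Latest visit (V = +14) | Earliest visit (V = −14) |
|---|---|---|---|
| 0 | 30 − 0 = 30 | 30 − 14 = 16 | 30 |
| 7 | 30 − 7 = 23 | 30 − 21 = 9 | 30 |
| 14 | 30 − 14 = 16 | 30 − 28 = 2 | 30 |

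The range over the allowed window is 2 to 30 days. Counting only visits on or after the decision, it is 16 to 30 days (L = 0), 9 to 23 (L = 7) and 2 to 16 (L = 14).

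A longer gap can close the window altogether. The rest week followed by the two-week delay for blood counts in Section 4.2.4 gives L = 7 + 14 = 21. Then U = 9 for a visit on the decision day, and U = 0 for a visit 9 or more days later.

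**Anchor of the 30-day contact**

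If Section 4.5 is read as counting from the decision, the contact falls on day 30 + L after the last dose: day 37 for L = 7 and day 44 for L = 14. Footnote 13 gives about day 30 in every case.

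**Is drug still present?**

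This is context only. Fraction remaining = 0.5^(t / half-life), assuming first-order decay. Section 1.2.4 puts the between-study mean half-life at about 3.6 to 4.7 days; the phase I study in Section 1.2.2 reports a "mean half-life of 4.7 days (range, 1.3 to 9.7 days".

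| Half-life | Day 7 | Day 14 | Day 30 |
|---|---|---|---|
| 3.6 days | 26% | 7% | 0.3% |
| 4.7 days | 36% | 13% | 1.2% |
| 9.7 days (slowest patient) | 61% | 37% | 12% |

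At the mean half-lives, the early part of the window still carries drug and the end carries almost none. These fractions are not adverse event rates.

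**After the change**

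With Toxicity Assessment also marked at a contact on or after day 30, U = 0 for every patient who is reached.

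**The case against.** The strongest reply is that other rules already cover most of what matters.

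- Section 9.1 follows every patient with an adverse event to resolution, return to baseline, another explanation or death. Section 4.7.1 has a similar rule. A reader of Section 4.5 alone might infer that only patients removed for an unacceptable event are followed. The documents do not support that: toxicity known at the end-of-treatment visit is followed in patients who stop for progression too.
- Serious events "through 30 days after the last administration of study drug, must be reported upon discovery or occurrence". A reader might infer that they go uncollected after the visit. They do not, although reporting on discovery still depends on the site hearing of them.
- Section 4.7 requires any event observed by the investigator, or observed or experienced by the patient, to be reported. The medication review near day 30 may bring some events to light. Under footnote 16, however, medication recording ends early if the next anti-cancer therapy starts.

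A reader might also infer that most of the window always goes unasked. That is true whenever the last dose is on the decision day, and for a visit on the decision day at each of the three gaps in the table. It is not true in every allowed case: a late visit can leave 9 or 2 days, or none. Nor do the documents show how patients will be distributed over these cases.

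Finally, Section 8 sets no time window for the toxicity table, and nothing in the documents gives the rate of new events after stopping. A bias of known size cannot be claimed.

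These points narrow the concern but do not remove it. None of them schedules a question about new events after the end-of-treatment visit.

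**Conclusion.** The mismatch is real. Followed as written, the plan requires 30 days of adverse event reporting after the last dose, but its last scheduled toxicity assessment leaves about 2 to 30 of those days uncovered for gaps of up to 14 days between last dose and decision. The figure is 16 to 30 days if the visit is on the decision day.

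What is exposed is limited to new, mainly non-serious events starting after that visit. They rely on spontaneous report, so the secondary toxicity counts can be too low by an amount the documents do not let us estimate. The primary response rate is untouched. This is a low-cost improvement to ascertainment, not a flaw that threatens the trial's main conclusion.

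The calculation rests on the chosen gaps of 0, 7 and 14 days and on reading the empty Follow-Up cell as no assessment planned there. The second reading is supported by the same column being filled in for medications and survival.

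**What to change.** In the Section 7.1 schedule, mark Toxicity Assessment (footnote 5) in the Follow-Up column, limited to the existing contact about 30 days after the last dose. State that this contact is held on or after day 30, so that the whole window has passed when the question is asked. The later follow-up contacts need no change.

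Reconcile the starting point of that contact between Section 4.5 (discontinuation of treatment) and footnote 13 (last dose). Counting from the last dose would match the reporting window in footnote 5.

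The cost is a schedule edit, a few minutes per patient at a contact that already takes place, and the extra adverse event pages. Reported counts may rise slightly. Patients who die or are lost before the contact will still have an incomplete window.

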4.2 Study Drug Administration: Tivozanib

- 4.2.1 Drug Dispensing: The patient will be dispensed enough pills for 1 cycle at each monthly visit. Patient pill calendar will be reviewed by study coordinator or nurse. Pill count will be done, and any unused pills will be returned each cycle.
- 4.2.2 Dosing Schedule: Tivozanib hydrochloride will be administered orally, at a dose of 1.5 mg/day, beginning on Day 1 of Cycle 1. Subjects will receive tivozanib hydrochloride once daily for 3 weeks followed by 1 week off treatment. One cycle is defined as 4 weeks. Cycles will be repeated every 4 weeks in the absence of disease progression or unacceptable toxicities.
- 4.2.3 Dosing Information: The prescribed daily dose of tivozanib hydrochloride is to be taken, once per day, preferably in the morning, with water. Tivozanib should be taken on an empty stomach either 1 hour before or 2 hours after meals at the same time each day. The tablets should be swallowed whole and cannot be crushed or broken. Only one capsule of tivozanib hydrochloride should be taken each day. If a dose is vomited or otherwise missed that day for any reason, the dose for that day should not be made up. The next dose should be taken as prescribed at the next scheduled time (i.e., one capsule is to be taken even if the previous dose was vomited or otherwise missed; additional dose(s) should not be taken at any time to make up for any missed dose(s). Grapefruit and grapefruit juice should be avoided during the study.

In the event that tivozanib hydrochloride dosing is interrupted, the duration of cycle/treatment will not be extended; doses missed during the interruption will be captured as omitted rather than delayed.

4.2.4 Dosing Parameters: Subsequent cycles of therapy will not begin (day 1 of each cycle) until the ANC is ≥1500 cells/mcl and the platelet count is ≥ 100,000/mcl. Therapy will be delayed for a maximum of two weeks until these values are achieved. Patients who fail to recover adequate counts within a two week delay will be removed from study therapy. Grade 1 or 2 toxicity will not result in a dose reduction or treatment delay. Drug-related grade 3 or 4 toxicities will result in an interruption in treatment until the toxicity is less than or equal to grade 2. Additionally, a dose reduction will be performed. If there is no recovery to ≤ grade 2 or recurrent grade 3 or 4, then tivozanib will be discontinued.

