4.7.1 Tivozanib Hydrochloride Dose Modification

Clinical judgment will be used to determine appropriate management of the subject experiencing any adverse event (AE). The suggested criteria for dose modification for tivozanib hydrochloride drug-related AEs (excluding hypertension) are summarized in the table below.

Drug-Related	Action Taken	Subsequent Dosing Modification		
Adverse Events				
(excluding				
Hypertension ¹)				
Grade 1	No dose interruption, or reduction	None required; Dosing may continue		
	required; adverse event	at the same dose		
	management is at the discretion of			
	the Investigator			
Grade 2 No dose interruption, or reduction		None required; Dosing may continue		
	required; adverse event	at the same dose		
	management is at the discretion of			
	the Investigator			
Grade 3 ²	Interrupt dosing ³ until toxicity	Dosing may resume at same dose or		
	resolves to \leq grade 1.	reduced dose at the discretion of the		
		Investigator (see below for dose		
		reduction guidelines).		
Grade 4	Interrupt dosing until toxicity	Dosing may resume at same dose or		
	resolves to \leq grade 1.	reduced dose at the discretion of the		
	_	investigator (see below for dose		
		reduction guidelines).		

Tivozanib Hydrochloride Dose Modification Guidelines for Drug-Related Adverse Events

- 1. Hypertension must be treated as described in Appendix C prior to any dose modification
- 2. Referring to toxicity that persists despite appropriate medical care.
- 3. Tivozanib may be interrupted for up to 2 weeks. If a subject is able to resume treatment after an interruption of ≤ 2 weeks, missed doses will not be made up (i.e. the cycle duration will remain unchanged). If any drug related toxicity results in interruption of >2 weeks, the subject should be discontinued from study treatment unless there is clear benefit.

Patients should be followed for assessment of the toxicities until the AEs resolve or are deemed irreversible. The maximum delay of drug administration by the treating investigator or the patients' own decision for any reason, including toxicities, is 2 weeks. If the drug is withheld for more than 2 continuous weeks due to a treatment-related toxicity that does not resolve, the patient will be withdrawn from study treatment. The exception is HTN, which must first be treated as described in Appendix C prior to any dose modification.

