Patients will be withdrawn from the study if they fail to recover to grade ≤ 1 or tolerable grade 2 (or within 1 grade of starting values for pre-existing laboratory abnormalities) from a treatment-related toxicity within 2 weeks OR if they experience agent related adverse events requiring dose modification despite previous dose reductions (i.e. would require a 2nd dose reduction) unless the investigator agrees that the subject should remain in the study because of evidence that the patient is/may continue deriving benefit from continuing study treatment. The appropriate reduced dose will be determined after discussion with the principal investigator and approval of the Data Monitoring Committee. Patients requiring dose reductions should not have the dose re-escalated with subsequent treatments. If treatment was interrupted for < 1 week, the patient will resume dosing on the current treatment cycle. If treatment was interrupted for ≥ 1 week, the patient will start a new cycle of treatment.

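### Tumour imaging in the first 6 months follows treatment cycles, so permitted delays to cycle starts can stretch the 8-week scan interval to 10 weeks, or 12 at worst, and recorded PFS depends slightly on toxicity

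*Combined protocol and SAP*

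**What the plan says.** Section 7.1 defines the unit as "One cycle = 28 days", and footnote 11 schedules "CT scan or MRI or x-ray of chest-abdomen-pelvis every other cycle (or equivalent time frame for patients off treatment prior to disease progression"). This rule runs for the first 6 months, "then every 3 months thereafter until disease progression". The same footnote allows unscheduled imaging: "also repeat at any other time if clinically indicated based on symptoms or physical signs suggestive of progressive disease".

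Cycle starts can move. On recovery of neutrophils and platelets before a later cycle, Section 4.2.4 states: "Therapy will be delayed for a maximum of two weeks until these values are achieved". It sets no limit on how many cycles may be delayed. Section 4.7.1 adds that the maximum delay "for any reason, including toxicities, is 2 weeks".

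On interruptions within a cycle the protocol gives two answers. Section 4.2.3 and note 3 to the dose-modification table in Section 4.7.1 both leave the cycle length as it was. The closing text of Section 4.7.1 says: "If treatment was interrupted for ≥ 1 week, the patient will start a new cycle of treatment".

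Section 5.6 gives the endpoint: "Progression-Free Survival (PFS) is defined as the duration of time from study entry to time of progression or death, whichever occurs first". Section 8 plans a Kaplan-Meier estimate of PFS in the single arm and has no rule for assessments that fall off schedule.

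**The concern.** Radiological progression can only be dated to a scan that shows it. If the scan moves with the cycle, a patient whose next cycle is held for toxicity is also looked at later, and her recorded PFS lengthens for a reason unrelated to her tumour. There is no control arm in which such an effect could cancel.

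The gap is specific to patients on treatment. Footnote 11 already uses an equivalent time frame for patients off treatment and calendar months after month 6, but it does not say whether a patient on a dose hold counts as off treatment. The schedule foresees delayed cycles: footnote 15 gives CA-125 and ECG a rule for them. Imaging has none.

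**Working it through.** The plan states no scan interval in weeks and no PFS design figure, so there is no figure of its own to reproduce.

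**Interval.** Inputs: cycle of 4 weeks (Section 7.1); scan every second cycle (footnote 11); delay of 0 to 2 weeks per cycle start (Section 4.2.4).

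- No delay: 2 × 4 = 8 weeks.
- One full delay: 8 + 2 = 10 weeks.
- Full delays at both cycle starts, with the scan following the delayed start of the odd cycle: 2 × (4 + 2) = 12 weeks.

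**Mid-cycle interruptions.** If cycle length is unchanged (Section 4.2.3 and note 3 in Section 4.7.1), no scan moves. If a new cycle starts (closing text of Section 4.7.1), the interrupted cycle lasts the last dosing day plus the hold. Stopping after day 7 with a 7-day hold gives 14 days, and a scan interval of 2 + 4 = 6 weeks. Stopping after day 21 with a 14-day hold gives 35 days, and an interval of 5 + 4 = 9 weeks. The direction of the effect cannot be determined until these sections are reconciled.

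**Effect on PFS.** Assumptions: exponential true PFS with median m of 13, 17.3 or 26 weeks (3, 4 or 6 months; the documents give no value), and progression recorded at the next scheduled scan. Scans follow the grid up to week 26 and then every 13 weeks:

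- 8-week grid: weeks 8, 16, 24, 37, 50, ...
- 10-week grid: weeks 10, 20, 33, 46, ...
- 12-week grid: weeks 12, 24, 37, 50, ...

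With λ = ln 2 / m and scan times s₁ < s₂ < ... (s₀ = 0), mean lag = Σ sₖ[exp(−λsₖ₋₁) − exp(−λsₖ)] − 1/λ.

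| True median (weeks) | 8-week grid | 10-week grid | 12-week grid | 10 minus 8 | 12 minus 8 |
|---|---|---|---|---|---|
| 13 | 5.11 | 6.06 | 6.81 | 0.96 | 1.70 |
| 17.3 | 5.30 | 6.11 | 6.70 | 0.81 | 1.40 |
| 26 | 5.58 | 6.19 | 6.61 | 0.61 | 1.03 |

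A patient is on the 12-week grid only if every cycle start up to week 24 takes the full 2-week delay, so the last column is an upper bound.

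**Trial-wide mean shift** = fraction affected × (12 minus 8).

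- 18% affected: 0.18 × 1.03 = 0.19 to 0.18 × 1.70 = 0.31 weeks. The 18% is the share with dose interruptions for adverse events on tivozanib in the phase III renal trial (Section 1.2.3), borrowed here as an assumption.
- 50% affected: 0.5 × 1.03 = 0.52 to 0.5 × 1.70 = 0.85 weeks.

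**Recorded median.** This moves in steps. If every patient moved from the 8- to the 12-week grid, it would go from 16 to 24 weeks at a true median of 13, and stay at 24 at a true median of 17.3. With half the patients moved, it stays at 16 and 24 respectively.

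**The case against.** The strongest reply is that this is too small to matter. PFS is a descriptive secondary estimate in 30 patients, with no test and no comparator. With 30 events, a 95% interval for an exponential median runs from exp(−1.96/√30) = 0.70 to exp(1.96/√30) = 1.43 times the estimate, far wider than a shift of a few days. Twelve weeks needs the full delay at successive cycle starts. The delay rule in Section 4.2.4 concerns neutrophils and platelets, and low counts are not among the most frequent adverse events listed in Section 1.2.3. Section 4.2.4 also discontinues drug for recurrent grade 3 or 4 toxicity. Finally, scans are not the only route to progression: symptoms can trigger imaging, and exam and CA-125 are done every cycle, with CA-125 doubling counted as progression in Section 5.4.3.

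Most of this stands, and it is why the effect is called modest. It does not close the gap. Exam and CA-125 also follow the cycle, symptom-triggered scans miss silent progression, and no section anchors on-treatment scans to the calendar.

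Two stronger readings are tempting. A reader might infer that mid-cycle restarts shorten the interval to about 6 weeks. That relies on one of two conflicting rules, and even under that rule a late interruption lengthens the cycle. A reader might also put the added lag at 2.2 to 2.4 weeks per affected patient. That comes from running 8- and 12-weekly scans indefinitely, whereas footnote 11 switches to 3-monthly scans after 6 months.

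**Conclusion.** The point holds as a modest weakness in scan timing. On-treatment scan intervals in the first 6 months can run from 8 to 10 weeks, or 12 at worst, depending on toxicity-driven delay. The added mean lag is about 1.0 to 1.7 weeks per patient on a 12-week grid and about 0.6 to 1.0 weeks on a 10-week grid. Trial-wide it is about 0.2 to 0.3 weeks at 18% affected and at most about 0.9 weeks at 50%. These sizes rest on assumed exponential PFS, an assumed true median of 3 to 6 months, an assumed affected fraction, and detection by scheduled scan only. Unscheduled scans, exam and CA-125 make the real effect smaller.

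A reader might infer that the primary result is compromised. It is not: Section 8 counts CR or PR with no fixed assessment time, and neither the two-stage test nor the sample size uses the scan interval. The case for acting is that the remedy is cheap, not that the bias is large.

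**What to change.** In footnote 11, replace the every-other-cycle rule for the first 6 months with: *every 8 weeks from cycle 1 day 1, counted on the calendar and not shifted by dose delay, interruption or a restarted cycle*. Keep the schedule's existing visit window and the 3-monthly schedule after 6 months. For patients already scanned under the cycle-based rule, report actual scan intervals alongside PFS.

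Separately, Sections 4.2.3 and 4.7.1 must be reconciled on whether an interruption changes the cycle. The calendar anchor makes scan timing independent of how that is settled.

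Cost: a one-sentence amendment, with no new type of scan and no change to dosing rules. Some scans will no longer coincide with a delayed day-1 visit. Patients enrolled before the amendment will have followed the old schedule, so the trial will contain both; Section 8 records that 9 evaluable patients had been reviewed by October 2016.
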